5.1.3.2 Blinding

The study is a double-blind study using DS-5565 and placebo, which will be prepared to be indistinguishable in appearance from the investigational product. The study will be blinded for those who will be involved in the study (subjects, investigators, sub-investigators, other staff members related to the clinical study, the sponsor, etc.), with the exception of the independent biostatistician, the independent sub-functional lead of

biostatistics (ISFLB), and staff members related to packaging operation and quality assurance.

Randomization schedule will be generated by the independent biostatistician and approved by the ISFLB. The independent biostatistician will share the randomization schedule with personnel specified in the randomization schedule request form for the investigational product assignment and keeping it strictly confidential until the study is unblinded.

Until the study is unblinded, the person responsible for investigational product monitoring at the drug concentration monitoring facility will use a different identification number from the subject identification code and the study drug identifier to maintain blinded manner when reporting the outcome of measurements to the sponsor.

5.1.3.3 Preparation and Management of Emergency Codes

Independent biostatistician or ISFLB will prepare emergency codes that can be unblinded by the study drug identifier, so that administered treatment of the patient can be identified in case of emergency.

The emergency codes will be retained in dedicated IWRS managed by Bell Medical Solutions, Inc.

The emergency codes must not be unblinded for the cases other than the states of Section 5.1.3.4.

5.1.3.4 Procedures for Emergency Unblinding

- 1) If emergency unblinding is deemed necessary by the investigator or sub-investigator:
 - When it is deemed necessary to unblind the treatment assignments to treat AEs, the investigator or sub-investigator will request the sponsor to determine the appropriateness of the emergency unblinding after explaining the reason through the IWRS.
 - The sponsor will determine the appropriateness of the emergency unblinding in consultation with medical expert as required.
 - i. When emergency unblinding is deemed appropriate by the sponsor**
 - When unblinding is deemed appropriate, the sponsor will notify the

investigator or sub-investigator of the fact and the reason through the IWRS.

- The sponsor will request the investigator or sub-investigator to prepare the CRF of the appropriate patient.
- The sponsor issues the password for confirming the emergency code of the appropriate patient on the IWRS through the IWRS.
- The investigator or sub-investigator receive the password, enter their passwords to login, and then confirm the emergency code of the appropriate patient.
- Information about the treatment assignment **must be** restricted to only designated study site staff/personnel who are providing immediate care to the subject.
- Any documentation of the treatment assignment must be maintained separately (ie, a secured file). The information must not be included in the subject's source files to ensure the treatment assignment will remain blinded to the study monitor and other study personnel not involved with the subject's immediate care.

ii. When emergency unblinding is not deemed appropriate by the sponsor

- When unblinding is determined not appropriate, the sponsor will notify the investigator or sub-investigator of the fact and the reason through the IWRS.

2) When emergency unblinding is deemed necessary by the sponsor

- When emergency unblinding is deemed necessary in consultation with medical expert in case of such as occurrence of a potential safety problem for the patients, the sponsor will notify the investigator or sub-investigator of the unblinding.
- The sponsor will request the investigator or sub-investigator to prepare a CRF of the appropriate patient.
- The sponsor relies the issuance of the password for confirming the emergency code of the appropriate patient on the IWRS to the investigator or sub-investigator through the IWRS.
- The sponsor receives the password, enters the password to login, and then confirm the emergency code of the appropriate patient.

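### A site that needs the treatment code to manage an adverse event can see it only with the sponsor's prior agreement, which may be refused and has no stated response time

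*Combined protocol and SAP*

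**What the plan says.** Section 5.1.3.3 has emergency codes prepared "so that administered treatment of the patient can be identified in case of emergency". They are held in the IWRS, and the same section forbids breaking them except as Section 5.1.3.4 provides.

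Section 5.1.3.4(1) covers a request from the site. When a physician there considers that the assignment must be known to treat an AE, "the investigator or sub-investigator will request the sponsor to determine the appropriateness of the emergency unblinding", giving the reason in the IWRS. Next, "The sponsor will determine the appropriateness of the emergency unblinding in consultation with medical expert as required". Two branches follow:

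- **Sponsor agrees (i).** The sponsor notifies the site, asks for the subject's CRF to be prepared, and "The sponsor issues the password for confirming the emergency code of the appropriate patient on the IWRS through the IWRS". The physician then logs in and reads the code. The assignment is confined to site staff giving immediate care and is filed apart from the source records.
- **Sponsor disagrees (ii).** "When unblinding is determined not appropriate, the sponsor will notify the investigator or sub-investigator of the fact and the reason through the IWRS". Nothing further is provided.

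Section 5.1.3.4(2) covers unblinding that the sponsor starts. It ends with: "The sponsor receives the password, enters the password to login, and then confirm the emergency code of the appropriate patient".

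Section 5.1.3.2 counts the sponsor among the blinded parties. Its exceptions are the independent biostatistician, the independent sub-functional lead of biostatistics, and packaging and quality-assurance staff.

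**The concern.** A code-break procedure exists for the occasion when someone treating a subject needs the assignment quickly. Here the person at the bedside makes that judgement, and a remote party that is itself blinded then makes it again. No criteria are given for the second judgement, and it can end in refusal.

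The occasions are foreseeable from the protocol itself. Section 1.3 lists suicide and hepatic transaminase elevations among notable events seen in earlier studies, and effects of CNS depression among anticipated risks. Section 4.2.4 sets study stopping rules for hepatic events and for suicide. Subjects are outpatients who take the product themselves (Section 5.1.4), at approximately 200 sites in four countries (Section 3.1.1).

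What is at stake is a site's ability to act on its own clinical judgement about needing the code. There is also a smaller question of who at the sponsor may read a code under 5.1.3.4(2).

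**Working it through.** No arithmetic applies. The point depends on no sample-size, power or error-rate input, so the check sets the relevant sections side by side.

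1. **Is prior agreement required?** Yes. In 5.1.3.4(1) the request goes to the sponsor, which decides before any code is released.
2. **Can the site reach the code without a sponsor act?** No. After agreement, access still needs a password that the sponsor issues.
3. **Can the sponsor refuse?** Yes. Branch (ii) is written for that outcome. It provides notice and a reason, with no appeal and no override.
4. **Is there a time limit?** None appears in Sections 5.1.3.2 to 5.1.3.4 or elsewhere in the supplied text. The protocol sets clocks in other places: 24 hours for SAE reports from site to sponsor (Section 9.2), and 3 days for the DSMB to notify the sponsor after a meeting (Section 11.9).
5. **Is there another route?** No. Section 5.1.3.3 closes off breaks outside 5.1.3.4, and 5.1.3.4(2) begins only when the sponsor considers unblinding necessary.
6. **Does this meet the stated purpose?** Section 5.1.3.3 wants treatment to be identifiable in an emergency. Suppose the site judges that it has such an emergency and the sponsor disagrees, or does not answer in time. Followed exactly, 5.1.3.4 then leaves the treatment unidentified. The purpose is met only when the sponsor agrees promptly, and nothing in the text ensures that.
7. **Who sees the code?** In the site-initiated route the physician reads it, and the text does not show it to the sponsor. In the sponsor-initiated route the sponsor reads it, although no exception in Section 5.1.3.2 names a sponsor safety function.

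**The case against.** The strongest defence has four parts.

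- **There is no strict contradiction.** Section 5.1.3.3 does not say on whose authority treatment is to be identified, and it refers to 5.1.3.4 for that. This is correct. The point is that the procedure does not secure its purpose, not that the two sections cannot both be true.
- **Emergency cover may exist.** The contents list a contract research organization for emergency contact (15.10.4.6), but the text of that section was not available. Hours of cover therefore cannot be checked, and a claim that no one would answer at night would be unsupported. Cover bears on delay only. Section 5.1.3.4 gives that organization no role, and cover would leave the approval step and the refusal branch in place.
- **Care does not stop without the code.** The investigator may end a subject's participation at any time (Section 4.2) and gives appropriate treatment for AEs and SAEs (Sections 9.1.4 and 9.2). The liver withdrawal criteria and work-up (Sections 4.2.1 and 9.4) apply whatever the assignment. This stands, and it limits what can be said about harm. It does not answer the case that 5.1.3.4(1) itself describes, in which the physician has already concluded that the assignment is needed.
- **Sponsor review protects the blind.** It may prevent some unnecessary breaks. Logging and the existing confidentiality rules can keep breaks visible and contained without a veto.

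A reader might infer three stronger things that the documents do not support. First, that a site can never learn the treatment: it can, once the sponsor agrees and issues the password. Second, that a completed CRF is a precondition for the password: the sponsor asks for the CRF to be prepared, but the text does not make release conditional on it. Third, that every site-requested break exposes the assignment to sponsor staff: only the sponsor-initiated route shows the sponsor reading a code.

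**Conclusion.** The concern holds in this form. An investigator who has judged unblinding necessary to treat an AE depends on the sponsor's prior agreement and on a sponsor-issued password. Refusal is allowed, and the supplied text gives no response time, no override and no other route.

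The rule applies to every subject in the double-blind study, planned at approximately 750. That is the reach of the rule, not a forecast of code breaks or of harm; the documents give no basis for either.

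Confidence is high on the approval step and the refusal branch, which are written rules. It is lower on delay, because the emergency-contact arrangements could not be read. The conclusion rests on the protocol's own stated purpose for the codes and needs no outside standard.

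The sponsor's sight of the code in 5.1.3.4(2) is a separate and lesser point. The text does not say which sponsor function is meant. Section 11.9 shows that a clinical safety and pharmacovigilance role exists, so this is a gap to close and not evidence that study staff would be unblinded.

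**What to change.** Amend Section 5.1.3.4(1) as follows:

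- The investigator or sub-investigator can break the code directly in the IWRS when knowledge of treatment is needed to manage the subject.
- Contact with the sponsor is encouraged but is not a condition, and branch (ii) is deleted.
- The IWRS records user, date and reason, and alerts the sponsor that a break has occurred without showing the assignment.
- CRF completion follows the break.
- The existing rules on who may know the assignment and where it is filed stay as they are.

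Section 5.1.3.3 can stand, because it already defers to 5.1.3.4.

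In Section 5.1.3.4(2), state that the code goes only to a named safety function outside the study team, and add that function to the exceptions in Section 5.1.3.2.

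If the sponsor keeps a step of its own, the protocol should at least say who holds the final decision, what access the site has without sponsor release, and the longest time allowed for an answer.

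The cost is a short protocol amendment and a change of IWRS permissions. The downside is possibly a few more code breaks, each logged and countable.

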5.1.3.5 Subject Replacement

No subjects will be replaced in this study.

5.1.4 Method of Assessing Treatment Compliance

All subjects in this study will commence therapy as outpatients, and the investigational product will be self-administered orally. Subjects will be sent home with the investigational product. Each subject is to return the investigational product at every visit. Compliance will be assessed by returned tablet count. Administration of the investigational product will be recorded in the eCRF/Drug Accountability Record (number of tablets taken) at all treatment visits. If no tablets are returned, the subject will be asked whether any were discarded or thrown away, or if all of the tablets were taken orally.

5.1.5 Labeling and Packaging

DS-5565 and/or matching placebo, will be packaged in aluminum blister packs. Packages for the treatment period will be prepared for the combinations shown in Table 5-2, Table 5-3, and Table 5-4. One box will be prepared for each subject. Each box will contain the investigational product for that subject during the treatment period. The packaging will be clearly labeled "For Clinical Study Use Only," and will show the display name of the investigational product, the investigational-product-manufacturing code, the study drug identifier, the name and address of the sponsor, and the expired date of the investigational product in accordance with local regulations. Each wallet card of the investigational product will contain sufficient extra doses to cover the permitted visit window for each subject.

Table 5-2 Drug Combinations During the Treatment Period (Week 1)

Treatment group	Investigational product combination	
	Morning	Bedtime
DS-5565 15 mg QD	(P)	(5)
DS-5565 10 mg BID	(5)	(5)
DS-5565 15 mg BID	(5)	(5)
Placebo	(P)	(P)

(P) DS-5565 matching placebo tablet

(5) DS-5565 5 mg tablet

Table 5-3 Drug Combinations During the Treatment Period (Week 2)

Treatment group	Investigational product combination	
	Morning	Bedtime
DS-5565 15 mg QD	(P)	(10)
DS-5565 10 mg BID	(10)	(10)
DS-5565 15 mg BID	(10)	(10)
Placebo	(P)	(P)

(P) DS-5565 matching placebo tablet

(10) DS-5565 10 mg tablet

Table 5-4 Drug Combinations During the Treatment Period (Week 3 to Week 14)

Treatment group	Investigational product combination	
	Morning	Bedtime
DS-5565 15 mg QD	(P)	(15)
DS-5565 10 mg BID	(10)	(10)
DS-5565 15 mg BID	(15)	(15)
Placebo	(P)	(P)

(P) DS-5565 matching placebo tablet

(10) DS-5565 10 mg tablet

(15) DS-5565 15 mg tablet

5.1.6 Storage

Up to 25°C; do not freeze (excursion permitted up to 30°C).

5.1.7 Drug Accountability

The sponsor will deliver the investigational product as needed to the investigational product administrator designated at the study site. The administrator will store and manage the investigational product based on the manual for management of investigational product, and will maintain records and prepare reports as required.

5.2 Concomitant Medications and Treatments

Any concomitant medications except rescue medication (see Section 5.2.3) and any concomitant treatments conducted to a subject during the period from the time of obtaining informed consent until Visit 11, whether permitted or not, will be documented in the CRF. The route of administration, the total daily dose, the duration of use, the indication for use, and the classification of therapies will also be documented in the CRF.

5.2.1 Prohibited Concomitant Medications

The following drugs are prohibited for concomitant use from the screening (Visit 1) through the post-treatment follow-up (Visit 11). The patients given drugs that could

cause irreversible retinal degeneration must be excluded. After informed consent is obtained, subjects who are under treatment with the following prohibited concomitant drugs will undergo a washout period of 7 days or more. Visit 1 will occur after completion of this washout period.

- 1) Pregabalin
- 2) Antiepileptics (gabapentin, carbamazepine, etc.)
- 3) Antidepressants (other than selective serotonin reuptake inhibitors)
- 4) Hypnotics, anxiolytics (other than ultrashort acting drug [triazolam, zopiclone, zolpidem tartrate])
- 5) Opioids
- 6) Tramadol
- 7) Neurotrophin[®]
- 8) N-methyl-D-aspartate receptor (NMDA) antagonists (dextromethorphan, ketamine, memantine, etc.)
- 9) Non-steroidal anti-inflammatory drugs (except topical product for other than disease site of DPN)
- 10) Muscle relaxants
- 11) Topical capsaicin (except topical product for other than disease site of DPN)
- 12) Local anesthetics (lidocaine, etc.) (except topical product for other than disease site of DPN)
- 13) Na channel blockers (mexiletine, etc.)
- 14) Centrally acting sympatholytic agents (clonidine, etc.)
- 15) Steroids (except topical product for other than disease site of DPN)
- 16) cilostazol, prostaglandin (except topical product for other than disease site of DPN)
- 17) Chinese herbal medicines with analgesic effects on neuropathic pain (Life-preserving kidney-qi pill, Peony and licorice decoction, Eight-ingredient pill with rehmannia, etc.)
- 18) Vitamins B1 and B12 (except topical product for other than disease site of DPN)
- 19) α -lipoic acid
- 20) γ -linolenic acid (evening primrose oil)
- 21) Aldose reductase inhibitors
- 22) Drugs that could cause irreversible retinal degeneration (phenothiazine antipsychotics, deferoxamine, quinine, quinidine, ethambutol, voriconazole, etc.)
- 23) Other investigational products

5.2.2 Restricted Concomitant Medications

The following drugs are permitted for concomitant use if their dosage has not changed for 30 days prior to Visit 1. These drugs may be used concomitantly from the screening (Visit 1) through the post-treatment follow-up (Visit 11), but the dosage may not be changed.

- 1) Antidiabetic drugs other than insulin
- 2) Selective serotonin reuptake inhibitors (limited to the treatment of depression and anxiety)
- 3) Hypnotics (only ultrashort-acting drugs [triazolam, zopiclone, zolpidem tartrate])
- 4) ameliorator for peripheral circulation (except for cilostazol and prostaglandin)
- 5) Aspirin (only for preventing thrombosis and embolism [eg, myocardial infarction and stroke], should be used according to the package insert)

5.2.3 Rescue Medications

Acetaminophen will be permitted as a "rescue medication," to be used as needed only, and not to exceed the maximum dose stipulated in the package insert. Each subject should record dose(s) of acetaminophen used in the electronic patient diary from Visit 1 to Visit 10, if he/she takes acetaminophen.

5.2.4 Prohibited Concomitant Therapies

Concomitant use of the following therapies is prohibited from the screening (Visit 1) through post-treatment follow-up (Visit 11).

- 1) Nerve blocks
- 2) Laser therapy
- 3) Acupuncture treatment
- 4) Spinal cord stimulation
- 5) Surgery that might confound the assessment of DPNP
- 6) Electrical stimulation therapy
- 7) Other forms of pain reduction therapy that might confound the assessment of DPNP

5.2.5 Other

Subjects should be instructed to avoid excessive consumption of alcohol during the treatment period, as the investigational product may increase side effects of sleepiness and dizziness and potentiate the impairment of motor skills.

6. STUDY PROCEDURES

A study visit schedule in tabular format is provided in section 17.1.

In principle, all of the activities and/or examinations will be recorded with the date in the CRF.

Missing visits are strongly discouraged in this study. It is expected that investigator site staff thoroughly explain the visit schedule with potential subjects. If it is felt that a subject is not able to adhere to the visit schedule, then that subject should not be randomized into the study. Any missed visit that occurs during the double-blind treatment period must be rescheduled within 1 week.

6.1 Screening (Visit 1, 7 days prior to randomization)

Written informed consent will be obtained before screening. If prohibited concomitant drugs are used within 7 days before obtaining informed consent, screening activities will follow a washout period of at least 7 days. Therefore, in this case, written informed consent must be obtained before entering the washout period. The following activities and/or examinations will be performed at screening.

- Evaluate inclusion criteria and exclusion criteria
- Record demographics (birth date, sex, type of diabetes, duration of diabetes, duration of DPN, duration of DPNP), medical/surgical history related to exclusion criteria and alcohol history
- Provide explanation regarding electronic patient diary, and providing of electronic diary
- Complete SF-MPQ
- Complete HADS
- Measure body height and weight
- Perform physical examination
- Perform evaluation of edema
- Perform full neurological examination
- Perform ophthalmologic examination
- Measure blood pressure and pulse rate
- Perform 12-lead ECG
- Collect blood and urine samples for laboratory tests
- Collect blood sample for evaluation of fasting blood glucose levels
- Collect blood sample for evaluation of HbA1c

- Evaluate AEs
- Complete C-SSRS
- Perform pregnancy test (only in women of childbearing potential)
- Evaluate prior drug treatment, concomitant drugs, and concomitant therapy
- Complete Module A and B on MINI Interview (Version 6.0)

6.2 Randomization (Visit 2, Day 1)

Subjects will be randomized to treatment groups after screening. The following activities and/or examinations will be performed at randomization.

- Evaluate inclusion criteria and exclusion criteria
- Review electronic patient diary data
- Complete SF-MPQ
- Complete the modified BPI-SF
- Complete MOS sleep scale
- Complete HADS
- Complete 36-item short form health survey (SF-36)
- Measure body weight
- Perform physical examination
- Perform abbreviated neurological examination
- Measure blood pressure and pulse rate
- Collect blood and urine samples for laboratory tests
- Evaluate AEs
- Complete C-SSRS
- Record and evaluate concomitant drugs and concomitant therapy
- Confirm eligibility and randomization
- Issue the investigational product
- Select and record the drug administration in the morning (fasted/fed) during the study treatment

6.3 Treatment Period

The treatment period will be 14 weeks in duration.

6.3.1 Visit 3 and Visit 4

From Visit 2 to Visit 4, subjects will come to the study site every week (Visit 3, Visit4). The investigator or sub-investigator will confirm tolerability and review continuation of

the treatment before issuing the new investigational product. The following activities and/or examinations will be performed at Visit 3 and Visit 4.

- Review electronic patient diary data
- Complete SF-MPQ
- Complete HADS
- Measure body weight
- Perform physical examination
- Perform abbreviated neurological examination
- Measure blood pressure and pulse rate
- Collect blood and urine samples for laboratory tests
- Evaluate AEs
- Complete C-SSRS
- Record and evaluate concomitant drugs and concomitant therapy
- Collect unused investigational product, and record and review drug-taking compliance
- Record the date of the first dose taken
- Issue the investigational product
- Collect blood sample for PK analysis

6.3.2 Visit 5, Visit 6, Visit 7, Visit 8, and Visit 9

From Visit 4 to Visit 9, subjects will come to the study site once every 2 weeks (Visit 5, Visit 6, Visit 7, Visit 8, and Visit 9). The investigator or sub-investigator will confirm tolerability and review continuation of the treatment before issuing the new investigational product. The following activities and/or examinations will be performed at Visit 5, Visit 6, Visit 7, Visit 8, and Visit 9.

- Review electronic patient diary data
- Complete SF-MPQ
- Complete HADS
- Measure body weight
- Perform physical examination
- Perform abbreviated neurological examination
- Measure blood pressure and pulse rate
- Collect blood and urine samples for laboratory tests
- Collect blood sample for evaluation of HbA1c (Visit 6 only)
- Collect blood sample for evaluation of fasting blood glucose levels (Visit 6 only)

- Evaluate AEs
- Complete C-SSRS
- Record and evaluate concomitant drugs and concomitant therapy
- Collect unused investigational product, and record and review drug-taking compliance
- Issue the investigational product
- Collect blood sample for PK analysis (Visit 6 and Visit 8 only)

